- Subjects who plan to undergo total joint replacement during the study will be discontinued from the treatment period and entered into Early Termination Follow-up (See Section 6.9) until their joint replacement or other arthroplasty procedure. For these subjects, a complete early termination visit (which includes all Week 56 and Week 64 activities) should be conducted prior to the total joint replacement or arthroplasty procedure (Section 6.9) and entrance into the substudy or Study A4091064. Substudy or Study A4091064 Baseline visit activities (See Appendix 18, Schedule of Activities) should be completed on the same day as the early termination visit. Subjects who have not undergone or scheduled total joint replacement surgery within the investigational product or safety follow-up period of this study will not be eligible for the total joint replacement substudy or Study A4091064.

Subjects who undergo other types of joint replacement surgery or arthroplasty during the study should be discontinued from investigational product and complete the protocol specified Safety Follow-up Period but not be entered into the substudy or Study A4091064 for follow-up.

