For subjects discontinued prior to the Week 56 visit, follow-up radiographs of the hips, knees and shoulders should be performed as soon as possible (refer to Section 6.9.1) after the decision to withdraw from the study has been made, provided at least 30 days have passed since the last set of X-rays were collected. A final set of follow-up radiographs of the hips, knees and shoulders should be obtained 24 weeks (Early Termination Visit 3, Section 6.9.1.5) after the last dose of SC investigational product was administered. Any joint imaged at Screening or other at risk joints identified during the study period should also be imaged at Early Termination Visits 1 and 3.

For subjects who are identified by the Central Readers as having a possible or probable joint event (ie, rapidly progressive osteoarthritis, subchondral insufficiency fractures, spontaneous osteonecrosis of the knee [SPONK], primary osteonecrosis, or pathological fracture) and for subjects undergoing total joint replacement for any reason, all images and other source documentation will be provided to the blinded tanezumab Adjudication Committee for review and adjudication of the event. The Adjudication Committee's assessment of the event will represent the final classification of the event.

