7.4.5. Central Reader and Subject-Level Stopping Criteria for Joint Safety Events

Subjects identified through the measures described above (in Section 7.4.4) who are determined by the Central Reader to have possible or probable joint safety event (rapidly progressive osteoarthritis [type-1 or type-2]), subchondral insufficiency fractures (spontaneous osteonecrosis of the knee [SPONK]), primary osteonecrosis, or pathological

fracture will be withdrawn from treatment and enter the Early Termination Follow-up period (see [Section 6.9](#)).

The Central Reader will review the radiology images on an ongoing basis and provide assessments to the investigator and Pfizer. For subjects who are identified with a possible or probable event described above and for subjects undergoing total joint replacement for any reason, all images and other source documentation will be provided to the blinded tanezumab Adjudication Committee for review and adjudication of the event. The Adjudication Committee's assessment of the event will represent the final classification of the event (refer to [Appendix 14](#)).

Subjects with adverse event reports of rapidly progressive osteoarthritis (type-1 or type-2), subchondral insufficiency fractures (spontaneous osteonecrosis of the knee [SPONK]), primary osteonecrosis, or pathological fracture, will be withdrawn from treatment and enter the Early Termination Follow-up Period (see [Section 6.9](#)).

The Central Reader will review the Week 24 knee X-rays for evidence of radiographic progression of osteoarthritis. The Central Reader will identify subjects entering the study with asymptomatic knee osteoarthritis Kellgren Lawrence Grade 2 who progress to Kellgren Lawrence Grade ≥ 3 at Week 24. These subjects should be discontinued from tanezumab treatment and entered in the Early Termination Follow-up phase. Unless the Central Reader determines the subject has developed a joint condition that would warrant further evaluation by the Adjudication Committee such as rapidly progressive osteoarthritis, subchondral insufficiency fractures, spontaneous osteonecrosis of the knee (SPONK), primary osteonecrosis or pathological fracture, the images will not be further reviewed by the Adjudication Committee.

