9.5. External Adjudication Committee

A blinded Adjudication Committee consisting of external experts in orthopedic surgery, rheumatology, orthopedic pathology, or radiology with expertise in patients with end stage osteoarthritis and osteonecrosis will be convened. The Adjudication Committee will have written operating procedures and a Charter, including a specific description of the scope of their responsibilities. In general, the Adjudication Committee will be asked to review all possible or probable joint-related safety events identified by the Central Reader, total joint

replacement as well as investigator-reported adverse events of osteonecrosis, rapidly progressive osteoarthritis, subchondral insufficiency fracture (spontaneous osteonecrosis of the knee [SPONK]) or pathologic fracture. Adverse events related to joint safety that the investigator or sponsor considers medically important may also be reviewed by the Adjudication Committee. These will include, but will not be limited to events identified for adjudication by the Central Reader (see Section 7.4.5).

Prior to the Adjudication Committee's review of a given event, the Committee will be provided with blinded, available source documentation of progress reports from the investigator, orthopedic consult reports, operative reports, radiology reports, pathology reports, X-ray images, MRI images, and pathology specimens for review. Copies of all relevant clinical information including the items listed above should be provided to Pfizer or its designee for review by the external Adjudication Committee. Copies of the information should include the study number, site number and subject number, but it should not include the subject's name or initials.

The external Data Monitoring Committee (E-DMC) will be provided with a blinded summary of the Adjudication Committee's review of events after each review meeting.

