All events of total knee, hip or shoulder joint replacement will be reviewed by the Joint Safety Adjudication Committee (Adjudication Committee) established for the tanezumab clinical program. This Committee will adjudicate in an independent and blinded fashion if the event is primary osteonecrosis, worsening OA (further sub-divided into rapidly progressive OA (RPOA) type 1 or type 2, normal progression of OA or not enough information to distinguish between RPOA and normal progression of OA), subchondral insufficiency fracture, pathologic fracture, other (with diagnosis specified) or not enough information to specify a diagnosis. Prior to the Adjudication Committee's review of a given event, Committee members will be provided with blinded, available source documentation of progress reports from the investigator, orthopedic consult reports, operative reports, the pathology report from the central laboratory, radiology reports, DXA reports, x-ray images and MRI images for review. Sites will be requested to submit required source documentation to the Endpoint Management Team as soon as possible, and ideally within 29 ±5 days, after the total joint replacement surgery (ie, by the time the Week 4 visit occurs provided the source documentation has been completed). In addition, blinded summaries of the following data from Study A4091063 will be provided to the Committee members for review for each event undergoing adjudication: demographic and baseline characteristics, medical history and concomitant medications, study medication administration, non-drug treatments, subject disposition, efficacy data, adverse event information, neurological safety data and a serious adverse event narrative (if applicable).

The Adjudication Committee, in coordination with the Data Monitoring Committee (DMC), is responsible for ongoing analysis of these outcomes and for informing the sponsor of recommendations made.

Subjects, investigators, study coordinators, clinical site staff, orthopedic surgeons, clinical research associates (CRAs) staff directly involved with this substudy at Pfizer and its designees will be blinded to treatment assignment in Study A4091063. The data collected in this substudy will be combined with similar data collected in other tanezumab studies for analysis. Data analyses will be reported separately.

104. SUBSTUDY SUBJECT SELECTION

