This substudy can fulfill its objectives only if appropriate subjects are enrolled. The following eligibility criteria are designed to select subjects for whom the substudy is considered appropriate. All relevant medical and non-medical conditions should be taken into consideration when deciding whether this substudy is suitable for a particular subject.

104.1. Inclusion Criteria

Subject eligibility should be reviewed and documented by an appropriately qualified member of the investigator's study team (ie, the investigator or a sub-investigator) before subjects are included in this substudy.

Subjects must meet all of the following inclusion criteria to be eligible for enrollment into the substudy:

1. Evidence of a personally signed and dated informed consent document indicating the subject (or a legal representative) has been informed of all pertinent aspects of the substudy.
2. Subject has been randomized and treated with SC study medication in tanezumab Study A4091063 and has completed the study or has been withdrawn from the study.
3. Actual or planned total knee, hip or shoulder replacement surgery during tanezumab Study A4091063. Subjects undergoing total knee, hip or shoulder replacement surgery after the last subject completes the treatment period in Study A4091063 may be enrolled in Study A4091064 in order to complete the total joint replacement follow-up.

Note: additional procedures in a subject undergoing total joint replacement surgery (eg, revision of a previously replaced joint in addition to a new total joint replacement) will be allowed, but subjects undergoing solely sub-total arthroplastic procedures (eg, hemi-arthroplasty) will not be eligible.

4. Subject is willing and able to comply with scheduled visits and other substudy procedures.

104.2. Life Style Guidelines

All female subjects who, in the opinion of the investigator, are biologically capable of having children, and are sexually active, **who withdraw from Study A4091063 less than 16 weeks after the last dose of subcutaneous study medication** must agree to use two (2) methods of highly effective contraception **until 112 days (16 weeks) after the last dose of subcutaneous study medication**. Refer to Section 4.4 of the A4091063 protocol for guidance on appropriate methods of contraception.

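### Total joint replacement is the only surgery that by itself triggers adjudication or has its own endpoint, so an unplanned partial arthroplasty of a joint not recently imaged or not flagged can go unreviewed

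*Protocol*

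**What the plan says.** **Surgery as a trigger.** Protocol 7.3.8 states that "for subjects undergoing total joint replacement for any reason, all images and other source documentation will be provided to the blinded tanezumab Adjudication Committee", and 7.4.5 repeats the rule. Appendix 18, section 103, says the same of the substudy: "All events of total knee, hip or shoulder joint replacement will be reviewed by the Joint Safety Adjudication Committee". No other operation is named as a trigger.

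**Other routes to the committee.** Protocol 9.5 also gives the committee whatever the Central Reader calls a possible or probable joint event, and adverse events that the investigator reports as osteonecrosis, rapidly progressive osteoarthritis, subchondral insufficiency fracture or pathologic fracture. A last route is optional: "Adverse events related to joint safety that the investigator or sponsor considers medically important may also be reviewed by the Adjudication Committee".

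**Other arthroplasty.** Protocol 6.9.2 foresees it: "Subjects who undergo other types of joint replacement surgery or arthroplasty during the study should be discontinued from investigational product". These subjects complete safety follow-up but do not enter the substudy. Appendix 18, section 104.1, gives hemi-arthroplasty as its example: "subjects undergoing solely sub-total arthroplastic procedures (eg, hemi-arthroplasty) will not be eligible". Under Protocol 8.7 an operation is not itself an adverse event; only the condition behind it is reported.

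**SAP.** Sections 3.5.6 and 6.1.6 define and summarize adjudicated diagnoses, total joint replacement, and a combination of the two. Neither mentions partial arthroplasty.

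**The concern.** Joint-safety adjudication outcomes are a primary endpoint, and adjudicated events feed the joint-safety stopping rule (Protocol 9.6.1.3; SAP 7.2). Sending every total replacement to the committee, whatever the stated reason, means that detection does not rest on the local diagnosis. A partial procedure does not get that protection, although the choice between a total and a partial prosthesis is surgical and does not show whether rapidly progressive osteoarthritis, osteonecrosis or fracture lay behind it.

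At stake is a small number of events that could be the outcome of interest and never be classified. SAP 6.1.6 expects fewer than 10 total joint replacements in the substudy, so single cases matter.

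**Working it through.** The plan states no figure on this point, so there is none to reproduce. The check follows a partial arthroplasty through each route and then sizes one missed case.

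**1. Routes into adjudication**

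| Route | Source | What a partial arthroplasty needs |
|---|---|---|
| Surgery itself | Protocol 7.3.8, 7.4.5, 9.5 | Not available; total replacement only |
| Central Reader possible or probable event | Protocol 7.3.8, 7.4.5, 9.5 | A film of the native joint, and a flag |
| Investigator-reported adverse event | Protocol 9.5 | One of the named diagnoses |
| Referral by investigator or sponsor | Protocol 9.5 | A decision to refer; optional |

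**2. When a film of the native joint exists**

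- Scheduled: Screening and Weeks 24, 56 and 80, or Early Termination Visits 1 and 3 (Protocol 7.3.8). The longest nominal gap is 56 − 24 = 32 weeks.
- At-risk joint: a film is mandatory after severe joint pain lasting at least 2 weeks, or after another finding the investigator judges clinically significant (Protocol 7.4.4).
- Withdrawal: as soon as possible after the decision, if 30 days have passed since the last set (Protocol 6.9). For a planned operation this can precede surgery. For an unplanned one the decision to withdraw follows it.
- Visit before planned surgery: 6.9.2 calls for all Week 56 activities first, and Week 56 films go to the Central Reader (6.4.10). The sentence sits under planned total replacement, but its wording extends to arthroplasty. I read it as covering planned partial procedures. The separate paragraph on other arthroplasty sets no such visit.

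**3. The case that escapes**

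Take a subject with no flag on the last film who has a sudden event between films, receives a hemi-arthroplasty urgently, and is reported with a plain fracture or osteoarthritis term. The first three routes in the table fail and only optional referral is left. Later study films show the prosthesis. Because the subject is outside the substudy, the surgeon's assessment and the central pathology specimen (Appendix 18, 107.1 and 107.2) are not requested through it either.

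**4. Effect on the tables**

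If the case is not adjudicated, it enters no adjudicated-outcome row. Because it is not a total replacement, it does not enter that row either. The condition still appears among adverse events, and the stop of study drug still appears in disposition data if it fell in the treatment period.

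**5. Size of one missed case**

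Inputs: 66 subjects per arm, range 56 to 73 (Protocol 9.1); exact intervals by treatment group (SAP 6.1.6). One case in an arm is an illustration.

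For x events in n, the Clopper-Pearson limits are the 2.5% point of Beta(x, n − x + 1) and the 97.5% point of Beta(x + 1, n − x). For x = 0 the upper limit is 1 − 0.025^(1/n); with n = 66 this is 5.4%. For x = 1 the lower limit is 1 − 0.975^(1/n); with n = 66 this is 0.04%.

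| n | Case missed (x = 0) | Case captured (x = 1) |
|---|---|---|
| 56 | 0% (0 to 6.4%) | 1.8% (0.05 to 9.6%) |
| 66 | 0% (0 to 5.4%) | 1.5% (0.04 to 8.2%) |
| 73 | 0% (0 to 4.9%) | 1.4% (0.03 to 7.4%) |

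**The case against.** The strongest reply is that the plan's safety net is wider than its surgical trigger, and much of that stands.

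- A reader might infer that only total replacements go to adjudication automatically. They do not: every possible or probable event from the Central Reader goes too, whatever operation follows.
- A reader might infer that everything depends on the investigator's adverse event term. That overlooks the scheduled, at-risk-joint and withdrawal films, the visit before planned surgery, and the sponsor's own power to refer. A hospital admission for the underlying condition would normally be a serious adverse event, which the sponsor reviews blinded (Protocol 9.6.1.1).
- A reader might infer that such cases are lost from every joint-safety table. That needs three failures together: no Reader flag, a term outside the named list, and no referral. Once a case is adjudicated to a listed diagnosis it counts whatever the surgery, and SAP 3.5.6 says so for the combined endpoint. The stopping rule likewise counts adjudicated diagnoses; total replacement is not a component.
- A reader might take the line in Appendix 18, section 104.1, as a bar to adjudication. It governs entry to an observational substudy only.

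Protocol 9.5 also describes the committee's task in general terms and leaves its scope to a Charter that is not among the documents. The Charter may already cover any arthroplasty.

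What the reply does not remove is the unplanned procedure. A fracture might be judged a clinically significant finding that makes the joint at risk, but that is a judgement, and after surgery the film comes too late.

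**Conclusion.** The point holds in a narrow form. No visible text makes partial arthroplasty an adjudication trigger or an endpoint, although the protocol foresees it and stops study drug for it. Existing routes should capture most elective cases. The gap is mainly an unplanned partial procedure on a joint not recently imaged or not flagged, with an unlisted adverse event term.

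The documents give no rate of partial arthroplasty, so how often this happens is unknown and may be zero. One case per arm is an assumption, and the intervals in the table overlap heavily; they show the sensitivity of a sparse count, not a demonstrated bias. If a missed case in a tanezumab arm would have been adjudicated to a stopping-rule diagnosis, the difference in counts is one too low. The thresholds are redacted, so whether that could change a decision cannot be judged.

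**What to change.** In Protocol 7.3.8, 7.4.5 and 9.5, widen the surgical trigger from total joint replacement to any arthroplasty of a major joint, total or partial, for any reason. The protocol already defines a major joint in 7.3.2 and 7.3.8. In SAP 3.5.6 and 6.1.6, add a row by arm for any arthroplasty, total or partial. Keep the total joint replacement row and substudy eligibility unchanged, and align the Adjudication Charter.

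The cost is wording and an occasional extra case file for the existing committee, with no new visit or procedure. The change cannot supply a film that was never taken. Some cases may therefore end in the existing category for insufficient information (Appendix 14), but they would at least be reviewed and counted.

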Appendix 20. The Shoulder Pain and Disability Index (SPADI)

Shoulder Pain and Disability Index (SPADI)

Please place a mark on the line that best represents your experience during the last week attributable to your shoulder problem.

Pain scale

How severe is your pain?

Circle the number that best describes your pain where: 0 = no pain and 10 = the worst pain imaginable.

At its worst?	0	1	2	3	4	5	6	7	8	9	10
When lying on the involved side?	0	1	2	3	4	5	6	7	8	9	10
Reaching for something on a high shelf?	0	1	2	3	4	5	6	7	8	9	10
Touching the back of your neck?	0	1	2	3	4	5	6	7	8	9	10
Pushing with the involved arm?	0	1	2	3	4	5	6	7	8	9	10

Disability scale

How much difficulty do you have?

Circle the number that best describes your experience where: 0 = no difficulty and 10 = so difficult it requires help.

Washing your hair?	0	1	2	3	4	5	6	7	8	9	10
Washing your back?	0	1	2	3	4	5	6	7	8	9	10
Putting on an undershirt or jumper?	0	1	2	3	4	5	6	7	8	9	10
Putting on a shirt that buttons down the front?	0	1	2	3	4	5	6	7	8	9	10
Putting on your pants?	0	1	2	3	4	5	6	7	8	9	10
Placing an object on a high shelf?	0	1	2	3	4	5	6	7	8	9	10
Carrying a heavy object of 10 pounds (4.5 kilograms)	0	1	2	3	4	5	6	7	8	9	10
Removing something from your back pocket?	0	1	2	3	4	5	6	7	8	9	10

Appendix 4.3. painDETECT Questionnaire⁵58

1. VERSION HISTORY

Table 1. Summary of Changes

| Version/ Date | Associated Protocol Amendment | Rationale | Specific Changes |
|--------------------------|-------------------------------------|---|---|
| Original 25 Dec 2015 | Original 28 Aug 2015 | N/A | N/A |
| Version 2 14 Jun 2019 | Amendment 2 14 Sep 2017 | The changes reflect protocol amendment, updates from blinded data review and program decisions for alignment of analysis. Additionally, clarifications, removal of redundant/duplicated text have been implemented. | 
 • Various formatting and editorial clarifications were made (throughout). • Section 2.2: Updated the study design according to the change made in Protocol amendment 2. • Section 2.2: Clarified that most safety results will be presented for the treatment period. • Section 3.1 and 6.1: Specified the outcome of consultation as safety endpoints. • Section 3.2: Added change from baseline to Week 1 in low back pain intensity (LBPI). Added cumulative distribution of percent change from Baseline in RMDQ score to Weeks 16 and 56. Added usage of rescue medication (incidence, number of days of usage and amount taken) during Week 1. • Section 3.4: Modified description. Moved the description on how to summary baseline variables to Section 6.5.1. • Section 3.5.1: Clarified the Tier-1 events. Section 3.5.1: Changed the Tier-2 AE cutoff from 1% to 3%. Updated definitions for Abnormal Peripheral Sensation and Sympathetic Nervous System. A smaller set of the AEs of Sympathetic Nervous System (AEs of Decreased Sympathetic Function) is deleted. • Section 4: Clafied the definitions of analysis sets. • Section 5.2.1: Removed the calculation of treatment difference. Changed the calculation of 95% CI for response rate. • Section 5.2.2: Added mixed model ANCOVA for aLBPI and RMDQ. Removed the calculation of treatment differences, except for aLBPI and RMDQ ANCOVA analyses. • Section 5.2.3: Moved the description on NIS and PGA-LBP to section 6 with some modification. Removed the summary of WPAI parameters using categories. |

| | | | |
|--|--|--|---|
| | | | 
 • Section 5.3: Added the analysis with multiple imputation, BOCF and LOCF for the summary for LBPI, RMDQ, PGA and BPI-sf. • Section 6.1.1: P-value and 95% CI for risk difference will be shown for pooled Tier 1 adverse events and will not be shown for each adverse event within Tier 1 event. Updated the description of footnote for 3-tier AE tables. Removed the following analyses: Tier 1 and Tier 2 AE graphs, the comparison between the number of subjects with AEs of APS against the number of subjects with the AE of Oedema peripheral, the plots of the start and stop study day of specified individual AES of APS, the summary of start day and AE duration for five AEs of APS (Paraesthesia, Hyperaesthesia, Hypoaesthesia, Allodynia and Dysaesthesia), AEs of DSF and Oedema peripheral, summary of AEs and serious AEs by 1000 patient years of exposure, ‘incidence and severity’ table for decreased sympathetic function (DSF), and listing of AEs for subjects who are not randomized and those randomized and not treated. Added the summary for adverse events associated with laboratory abnormalities, vital signs, and ECG measurement. • Section 6.1.2: Changed the category of blood pressure. • Section 6.1.3: Removed the summary of mean change in postural blood pressure. Clarified the detail of analysis. • Section 6.1.6: Updated the analysis plan for joint safety adjudication outcomes and total joint replacement. • Section 6.1.7: Separate section (6.1.8) was made for outcome of consultation and moved the description on outcome of consultation to Section 6.1.8. • Section 6.1.9: Specified that ADA assessments will be made using all available data. • Section 6.1.10: Updated the analysis plan for physical examination. • Section 6.2: Clarified the definition of ‘on-treatment’ and ‘off-treatment’. |
|--|--|--|---|

| | | | |
|--|--|--|---|
| | | | 
 • Section 6.2.1: Added the ANCOVA analysis for change from baseline for aLBPI. Updated the description on handling of missing data based on the modification in section 5.3. Added plots of cumulative distribution of percent change from Baseline in aLBPI score. Removed the calculation of treatment differences in mean of change from baseline for aLBPI and in response rate in each aLBPI response category. Added the summary of change from baseline of aLBPI at Week 1. Removed the summary of proportion of subjects who meet a aLBPI response definition at Week 16. Added the description on the handling of aLBPI data obtaining after the early termination visit. • Section 6.2.2: Added the ANCOVA analysis for change from baseline for RMDQ. Added the description on handling of missing data based on the modification in section 5.3. Removed the calculation of treatment differences in mean of change from baseline for RMDQ. Added treatment response analysis for RMDQ. • Section 6.2.3: Updated the description on handling of missing data based on the modification in section 5.3. Removed the calculation of treatment differences in mean of change from baseline for PGA of LBP and in response rate in PGA of LBP response category. • Section 6.2.4: Updated the description on handling of missing data based on the modification in section 5.3. Removed the calculation of treatment differences in mean of change from baseline for BPI-sf. • Section 6.2.5: Removed the calculation of treatment differences in response rate in CLBP-RI. Added a plot of CLBP-RI analysis. • Section 6.2.7: Modified the description on analyses. • Section 6.2.8: Clarified the definition of event “discontinuation from treatment due to lack of efficacy”. • Section 6.2.9: Added usage of rescue medication (incidence, number of days of usage and amount taken) during Week 1. Clarified the summary of rescue medication. |
|--|--|--|---|

| | | | |
|--|--|--|---|
| | | | 
 • Section 6.2.10: Clarified the analyses for health care resource utilization. • Section 6.2.12: Removed the summary splitted by response to question 1. • Section 6.3.1: Clarified PK data summaries. • Section 6.3.2: Clarified NGF data summaries. • Section 6.3.3: Removed as biomarker data are not generated. • Section 6.4: Removed Subset analysis using NGF subset analysis dataset and biomarker subset analysis dataset. • Section 6.5.1: Added baseline summaries for diabetes status and painDetect score. • Section 6.5.2: Removed cumulative summary of discontinuation by treatment group and reason, study week of discontinuation, and summary table and listing of demographic details for subjects who are not randomized and those randomized but not treated. • Section 6.5.3: Modified the summary of study treatment exposure. • Section 6.5.4: Added NSAID use summaries. • Section 8: Updated the references. • Appendix 1: Updated the summary of efficacy analyses. • Appendix 2.1: Clarified the windows for various data types. • Appendix 2.3: Some modifications and clarifications were made. • Appendix 4.2: Added the details of the statistical method. • Appendix 4.3: Added the detail of painDETECT questionnaire. • Delete Appendix 5 (immunogenicity data reporting detail). |
|--|--|--|---|

| | | | |
|---------------------------------|------------|--|--|
| 
Version 3 4 Jul 2019
 | 
N/A
 | 
The changes reflect updates from blinded data review. Additionally, clarifications, removal of redundant/duplicated text have been implemented.
 | 
 • Section 5.2.2: Clarified the explanation on the ANCOVA analyses. • Section 6.1.4: Modified the explanation. • Section 6.1.7: Added the analysis on Neuropathy impairment score (NIS). • Section 6.2.1: Added the treatment difference of proportion of responder in weekly average LBPI score. • Section 6.2.6: Modified the descriptive statistics shown in the summary table. • Section 6.5.2: Modified the study week categories in the summary of time to discontinuation. • Section 6.5.3: Added the description on the summary of number of SC doses taken and duration in phases. Updated the description on the summary of oral study medication compliance. • Section 6.5.4: Added the description on the summary for treatments prior to start of study treatment. Clarified the summary for concomitant medications and non-drug treatments. • Appendix 1: Modified the time point for efficacy analyses. |
|---------------------------------|------------|--|--|

